2.3 RISK/BENEFIT ASSESSMENT

2.3.1 KNOWN POTENTIAL RISKS

Potential Physical Risks of Ascorbic Acid Infusion: dry mouth, nausea, vomiting, dizziness, headache, pseudohyperglycemia (if checked with point of care glucose testing), crystalluria.

Potential Psychological, Social, Legal Risks of Ascorbic Acid Infusion: No psychological, social or legal risks are identifiable from an extensive literature search.

Risks of Blood Draws: All patients will have blood drawn for research purposes. Most blood will be drawn through indwelling catheters. Risks of drawing blood percutaneously are uncommon and include bleeding and bruising.

Glucose Monitoring Plan:

Guidance for blood glucose monitoring in patients enrolled in the CITRIS-AH Trial:

Ascorbic acid is known to artefactually raise POC blood glucose readings by all POC devices except the StatStrip glucometer. However, it does not raise blood glucose readings from a basic metabolic panel or glucose results using the gas lab. Thus, extreme care must be taken to assure an accurate blood glucose level from a metabolic laboratory (BMP) or arterial blood gas panel before initiating any insulin therapy, including sliding scale or scheduled insulin.

Inpatient units not using the StatStrip POC glucometer should follow the guidelines below.

Guidance for blood glucose monitoring in patients enrolled this study:

- Critical care and Inpatient Unit (Main 9 West) Nursing and Physician leadership at all study sites must be informed of vitamin C’s effect on point of care (glucometer) blood glucose and arterial blood gas glucose point of care values.
- In-service training will be documented in the Study Training Log
- Bold signage will be displayed on all study instructions, data collection forms, and at the patient’s head of bed, stating:
 - ❖ STOP! Do not use Accucheck or other Point of Care devices to measure glucose on this patient
 - ❖ Use only metabolic or gas lab glucose screening methods
 - ❖ This patient is enrolled in a study with Vitamin C, which artefactually increases POC glucose testing
 - ❖ Do Not Initiate or Utilize Sliding Scale, Scheduled Insulin, or Continuous Insulin Infusion Without Laboratory Confirmation of Blood Glucose
- Those receiving insulin infusion or sliding scale insulin as a part of standard of care will have metabolic glucose screening on the schedule determined by the attending physician
- Blood glucose monitoring for insulin administration guidance should only be by a metabolic or blood gas laboratory measured blood glucose results, whether or not the study patient is receiving insulin
- Study personnel will follow each study patient closely to monitor insulin use to ensure that point of care glucose screening is suspended for the research subject.
- Point of care glucose testing may resume 36 hours after the last infusion of study drug.

2.3.2 KNOWN POTENTIAL BENEFITS

Most observational studies suggest a mortality benefit from prior or in-patient Vitamin C use after hospitalization for serious infections. None of the observational trials have reported significant Vitamin C-related toxicity. An animal model of acute lung injury with intravenous LPS and feces induced peritonitis demonstrate significantly less lung injury with Vitamin C, which may result in shortening the time patients require mechanical ventilation.

2.3.3 ASSESSMENT OF POTENTIAL RISKS AND BENEFITS

The identifiable risks arising from exposure to intravenous ascorbic acid infusion are low. In preliminary data analyzed at VCU for another intravenous Vitamin C in sepsis study, we extensively outlined the potential benefits brought by attenuation of acute lung injury and organ failure associated with bacterial sepsis. Given the low risk associated with ascorbic acid infusion and the potential high likelihood of benefit we assess the risk/benefit ratio to be low (i.e., that benefit far outweighs risk).

3 OBJECTIVES AND ENDPOINTS

| OBJECTIVES | ENDPOINTS | JUSTIFICATION FOR ENDPOINTS |
|---|--|---|
| Primary | | |
| Vitamin C infusion will significantly attenuate hepatic dysfunction as measured by the model for end stage liver disease (MELD) score | Change in MELD score at 96 hours as compared to baseline when compared to placebo. | MELD score is an independent positive predictor of mortality in patients with AH. |
| Secondary | | |

| OBJECTIVES | ENDPOINTS | JUSTIFICATION FOR ENDPOINTS |
|--|--|---|
| Vitamin C infusion will be safe and tolerable in patients with severe alcoholic hepatitis . | Documented side effects and serious adverse events at hours 24, 48, 96 when compared with hour zero in high dose ascorbic acid versus placebo. | AscA infusion may cause dry mouth, nausea, vomiting, dizziness, headache, flushing, rash, diarrhea. AscA can be excreted from kidney and lead to crystalluria, so will monitor urine pH via urinalysis. Will also monitor EKGs for QTc changes. |
| Secondary | | |
| Vitamin C infusion will attenuate biomarkers of inflammation (C-Reactive Protein, procalcitonin), vascular injury (Thrombomodulin, Angiopoietin-2), while inducing the onset of a fibrinolytic state (Tissue Factor Pathway Inhibitor) | Modulation of available biomarkers | Changes in these biomarkers may provide mechanistic insight into how vitamin C attenuates inflammation |
| Secondary | | |
| Vitamin C Infusion will improve clinical endpoints in this patient population . | 
Change in SOFA Score and Components at hours 48, 96, 168
 
Change in CLIF-SOFA scores and Components at hour 48, 96, 168 when compared to placebo
 
Change in MELD-Na, MDF, Lille scores at hour 48, 96, 168 when compared to placebo
 
Ascorbate level at hour 0, 48, 96, 168 (When feasible)
 
ICU-free days at day 28
 
All-cause mortality to day 28, 90
 
Hospital-free days at day 90
 | CLIF-SOFA, MDF, MELD, and Lille scores are associated with mortality in alcoholic hepatitis. Ascorbate levels are associated with mortality in sepsis patients in the ICU. AH patients have prolonged hospitalizations and are frequently in the ICU. |

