1 PROTOCOL SUMMARY

1.1 SYNOPSIS

Title: Vitamin C Infusion for Treatment In Sepsis and Alcoholic Hepatitis
Study Description: It is our long-term goal to identify relevant “druggable” targets for alcoholic hepatitis (AH) and to translate this knowledge in to effective strategies to prevent and treat AH. This proposal will focus on one key area of unmet need in the field i.e. those with alcoholic hepatitis who have active infection and sepsis.

Objectives: We hypothesize that in patients with sepsis and alcoholic hepatitis, a 96-hour infusion of vitamin C (ascorbic acid, AscA, 200mg/kg/24 hours) will improve hepatic function, be well tolerated, and will attenuate biomarkers of inflammation, vascular injury, and encourage fibrinolysis. To assess the efficacy of a 96-hour intravenous vitamin C infusion protocol (200 mg/kg per 24 hours) in patients with established alcoholic hepatitis (AH) and sepsis. In this course of performing this proof of concept phase II trial we will explore three hypotheses:

Hypothesis 1A: Vitamin C infusion will significantly attenuate hepatic dysfunction as measured by the model for end stage liver disease (MELD) score in patients with alcoholic hepatitis and sepsis.

Hypothesis 1B: Vitamin C infusion will be safe and tolerable in patients with alcoholic hepatitis and sepsis.

Hypothesis 1C: Vitamin C infusion will attenuate biomarkers of inflammation (C-Reactive Protein, procalcitonin), vascular injury (Thrombomodulin, Angiopoietin-2), while inducing the onset of a fibrinolytic state (Tissue Factor Pathway Inhibitor).

Endpoints:

Primary Endpoint: Change in MELD score at 96 hours as compared to baseline when compared to placebo.

Secondary Endpoints:

- SOFA Score and components at hours 48, 96, 168
 - PaO₂/FiO₂
 - SpO₂/FiO₂
 - Platelets
 - Total Bilirubin
 - Vasopressor status
 - Glasgow Coma Score
 - Creatinine or Urine Output
- CLIF-SOFA scores and components at hours 48, 96, 168
 - Total Bilirubin
 - Creatinine
 - Renal replacement therapy (yes/no)
 - West-Haven grade for hepatic encephalopathy (HE)
 - INR
 - Mean arterial pressure (MAP)
 - Use of vasopressors (yes/no)
 - PaO₂ or SpO₂
 - FiO₂
 - Use of mechanical ventilation (yes/no)
- Lille score
 - Age
 - Albumin (on admission)
 - Bilirubin (on admission, hour 96, 168)
 - Creatinine (on admission)
 - Prothrombin time (on admission)
- Maddrey Discriminate Function (MDF) at hours 96, 168
 - Prothrombin time (hours 96, 168)
 - Total bilirubin (hours 96, 168)

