 - PT control/reference level (assuming 12 seconds)
- Liver enzymes and function tests at hours 48, 96, 168
 - AST, ALT, total bilirubin, alkaline phosphatase, albumin
- MELD-Na Score at hours 48, 96, 168
 - INR, creatinine, bilirubin, sodium
- Documented tolerability at hours 24, 48, 96
 - Need for dose reduction, headache, dizziness, dry mouth, nausea, vomiting, flushing, rash, hypotension, treatment related adverse events
- Documented safety at hours 24, 48, 96
 - QTc Interval (EKG)
 - Crystalluria (Urinalysis with microscopy and pH testing)
- Serum Biomarkers
 - Procalcitonin, C-reactive protein, thrombomodulin, thromboelastography (TEG), Receptor for Advanced

Glycation End Products, Tissue Factor Pathway Inhibitor at study hours 0, 48, 96, 168 (When feasible)

- Ascorbate level at hour 0, 48, 96, 168 (When feasible)
- Need for escalation of support i.e. need for ventilator or pressor support when these are not needed at baseline
- ICU-free days at day 28
- All-cause mortality to day 28 and day 90
- Hospital-free days at day 90

Study Population: A total of 20 adult subjects with alcoholic hepatitis and suspected or documented sepsis will be enrolled in this study. All participants will be enrolled at the Virginia Commonwealth University Health System (VCUHS).

Phase: Phase II

[figure not shown]
Description of Sites/Facilities Enrolling Participants: Subjects will be recruited from the Emergency Department (ED), inpatient medicine unit admitted to the Digestive Health Service (DHS), and Intensive Care Units (ICU) at VCUHS.

[figure not shown]
Description of Study Intervention: Participants will be randomized to receive either intravenous Vitamin C (sterile L-ascorbic acid mixed in 5% dextrose in water) or placebo (5% dextrose in water). Active treatment will continue for 96 hours, discharge from study hospital, study withdrawal, or death, whichever comes first.

[figure not shown]
Study Duration: Years 1-4

[figure not shown]
Participant Duration: 90 days

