9.4 STATISTICAL ANALYSES

9.4.1 GENERAL APPROACH

Continuous variables will be compared across groups using ANOVA or a Kruskal Wallis ANOVA depending on their distribution. Changes from baseline to time of measurement will be compared by analysis of covariance. Categorical variables will be measured by Fisher's Exact test. Correlations will be assessed by Spearman's coefficient.

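### Four secondary scores are values in the synopsis and changes in Section 3, and Section 9.4.1 gives the two forms different tests; the liver tests, listed only as values, get no baseline adjustment

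*Combined protocol and SAP*

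**What the plan says.** The synopsis (1.1) lists, under secondary endpoints, "SOFA Score and components at hours 48, 96, 168", "CLIF-SOFA scores and components at hours 48, 96, 168", "MELD-Na Score at hours 48, 96, 168" and "Maddrey Discriminate Function (MDF) at hours 96, 168". None of these is worded as a change, although the same synopsis words the primary endpoint explicitly as a change in MELD from baseline. The liver enzyme and function tests are also listed there as values at hours 48, 96 and 168, and they have no entry in the Section 3 table.

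Section 3 lists the same four scores as changes. The SOFA entry reads "Change in SOFA Score and Components at hours 48, 96, 168". For CLIF-SOFA the table has "Change in CLIF-SOFA scores and Components at hour 48, 96, 168 when compared to placebo", and the line that covers MELD-Na and MDF reads "Change in MELD-Na, MDF, Lille scores at hour 48, 96, 168 when compared to placebo".

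Section 9.4.1 has two rules for continuous data. The first is "Continuous variables will be compared across groups using ANOVA or a Kruskal Wallis ANOVA depending on their distribution". The second sends changes from baseline to analysis of covariance, without naming the covariate. Section 9.4.2 covers the primary MELD endpoint only. No section assigns a form or a test to an individual secondary score.

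**The concern.** Whether a secondary score is adjusted for its baseline depends on which section the analyst follows. The synopsis form falls under the ANOVA/Kruskal-Wallis rule and the Section 3 form under the ANCOVA rule. Either choice could be defended as following the protocol, and nothing prevents it from being made after the data are seen.

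With 10 patients per arm, chance differences in baseline severity will often be sizeable, so the two analyses can reach different conclusions from the same data. Section 4.2 relies on secondary endpoints such as CLIF-SOFA to show changes in clinical outcome for proof of concept, so the ambiguity matters to how the trial will be read. The MDF hours also disagree between the two sections, and no reading of 9.4.1 resolves that.

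**Working it through.** **The plan's own figure.** Section 9.2 gives 8 per arm for MELD, from mean 29, SD 5, a 25% decrease, alpha 0.05 and 80% power. The difference is 0.25 × 29 = 7.25. Then n = 2 × (1.960 + 0.842)² × 5² / 7.25² = 7.5, which rounds up to 8. This reproduces and is not affected by the present point. The documents give no power figure for the secondary scores. Only the planned 10 per arm is carried forward.

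**The definitions side by side.**

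| Endpoint | Synopsis 1.1 | Section 3 | Test under 9.4.1 |
|---|---|---|---|
| SOFA, CLIF-SOFA, MELD-Na | value at 48, 96, 168 h | change at 48, 96, 168 h | ANOVA/Kruskal-Wallis or ANCOVA |
| MDF | value at 96, 168 h | change at 48, 96, 168 h | ANOVA/Kruskal-Wallis or ANCOVA |
| Liver enzymes and function tests | value at 48, 96, 168 h | not listed | ANOVA/Kruskal-Wallis |

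**Chance baseline imbalance.** In units of the baseline SD, the difference between arm means has standard deviation √(2/10) = 0.447. The probability that it exceeds 0.5 SD in either direction is P(|Z| > 0.5/0.447) = P(|Z| > 1.118) = 0.26. The mean absolute difference is 0.447 × √(2/π) = 0.36 SD.

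**Power.** The following are assumptions, not figures from the documents: a true effect of 1 SD at the follow-up hour, normal data with equal SDs, two-sided 0.05, and a baseline/follow-up correlation ρ.

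- Value compared by ANOVA: noncentrality = √(10/2) = 2.236 on 18 degrees of freedom, giving power of 56% at any ρ.
- ANCOVA on the hour-0 value: noncentrality ≈ 2.236 × √(16/17) / √(1 − ρ²) on 17 degrees of freedom. The factor 16/17 allows for estimating the slope.

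| ρ | ANOVA on value | ANCOVA, formula | ANCOVA, simulation |
|---|---|---|---|
| 0 | 56% | 53% | 55% |
| 0.3 | 56% | 57% | 58% |
| 0.5 | 56% | 66% | 66% |
| 0.7 | 56% | 82% | 82% |
| 0.8 | 56% | 93% | 92% |

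In 20,000 simulated trials per setting, the two tests disagreed on significance in 19%, 31% and 43% of trials at ρ = 0.5, 0.7 and 0.9.

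**Value or change under ANCOVA.** Let y be the follow-up value, x the hour-0 value and g the arm. If y = a + τg + βx + e, then y − x = a + τg + (β − 1)x + e. The treatment effect τ and its standard error are identical. Once the hour-0 value is a covariate, the choice between value and change no longer matters.

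**Skewed data.** For log-normal data (assumed log-SD 0.8, ρ = 0.5 and a 1 SD effect, all on the log scale), power is about 50% for ANCOVA on the raw scale and 56% for Kruskal-Wallis. It is about 67% for ANCOVA on the log scale and 63% for rank ANCOVA.

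**The case against.** The synopsis can be read as a list of measurements, inputs and hours with no stated contrast; it even lists age and an assumed control prothrombin time. On that view Section 3 defines the endpoints, and with 9.4.1 it already sends the four scores to ANCOVA. This is the more natural reading, and it stands for the four scores. It does not settle the liver tests, which Section 3 omits, or the MDF hours. It also relies on two things left unsaid: that the change in these rows is from baseline, and that the ANCOVA covariate is the baseline value.

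The power gain depends on a correlation that the documents do not give. It is nil up to about 0.3 and slightly negative at zero, and a weak correlation by hour 168 cannot be excluded. That stands, so the gain is conditional.

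A blanket move to untransformed ANCOVA would drop the plan's provision for non-normal distributions and could lose power on skewed laboratory values. That also stands and is met in the fix.

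A reader might infer that chance imbalance biases the unadjusted tests or inflates type I error. It does not: under randomisation the imbalance is already part of the unadjusted standard error. The cost is precision.

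**Conclusion.** The mismatch is confirmed for SOFA, CLIF-SOFA, MELD-Na and MDF, as is the disagreement on MDF hours. The liver tests, as written, receive an unadjusted comparison. The consequence is limited to the precision and consistency of secondary endpoints. If the baseline/follow-up correlation is 0.5 or more, baseline adjustment raises power from about 56% to at least 66% for a 1 SD effect at 10 per arm. Up to about 0.3 it makes no material difference. These figures rest on the assumed effect, correlations and normality.

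Two stronger readings are tempting and are not supported. One is that the plan commits to unadjusted tests for the four scores; Section 3 with 9.4.1 points the other way. The other is that this mismatch undermines the primary analysis; MELD is a change from baseline in both the synopsis and Section 3, and 9.4.2 assigns it ANCOVA. The point should be corrected, but the trial's main result does not depend on it.

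**What to change.** - In 1.1 and 3, use one definition for SOFA, CLIF-SOFA, MELD-Na, MDF and the liver tests: the value at each stated hour. Give MDF the same hours in both places. Its prothrombin time and bilirubin inputs are already scheduled at hour 48, so including that hour needs no new test.
- In 9.4.1, compare every continuous secondary endpoint that has an hour-0 value (those above, the biomarkers and ascorbate) between arms by ANCOVA, and name the hour-0 value as the covariate. Where the distribution is skewed, use the log scale or rank ANCOVA, and fix the rule for that choice before unblinding.
- Keep ANOVA/Kruskal-Wallis for endpoints with no hour-0 value, such as ICU-free and hospital-free days, and for Lille, which already uses admission values. Section 3 should then stop listing Lille as a change alongside MELD-Na and MDF.
- Record FiO₂ and ventilation status at hour 0 and at the follow-up hours. They are score components in the synopsis, but the schedule of activities does not name them at any hour.

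The cost is wording in three sections, two recorded items and one degree of freedom per model. If the correlation is near zero, power falls very slightly, from about 56% to 53–55% in the illustration.

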4 STUDY DESIGN

4.1 OVERALL DESIGN

Randomization of 20 subjects with AH and sepsis to receive either *Placebo* (50 ml of 5% dextrose in water every 6 hours for 96 hours, or 16 total doses) or *Vitamin C* (sterile L-ascorbic acid for injection at

200 mg/kg per 24 hours with entire calculated 24 hour dose diluted in 200 ml of 5% dextrose in water). One fourth of the 24 hour calculated dosage will be administered in 30 minute intravenous infusions and occur every 6 hours for a total of 16 doses. Standard of care therapy will be followed in both arms.

4.2 SCIENTIFIC RATIONALE FOR STUDY DESIGN

The purpose of this study is to assess the efficacy of intravenously infused ascorbic acid therapy for patients with alcoholic hepatitis (AH) and sepsis. By restricting the population to those we believe to have both infection and AH, this study targets a disease process and population that has the highest mortality rate and has been studied in animal models. By focusing on sepsis associated with AH, we have selected a group that has a higher disease burden than AH alone and thus likely to have both increased mortality and an increased opportunity for benefit, including a reduction in hepatic dysfunction and ICU length of stay. In choosing the MELD score as the primary outcome, we will be able to discriminate between hepatic function improvement and risk of mortality. By using secondary endpoints such as CLIF-SOFA, documentation of serious adverse events, and biomarkers of inflammation, vascular injury, and coagulation, as the primary outcomes, we will be able to detect changes in clinical outcomes, assess safety and tolerability of ascorbic acid therapy in alcoholic hepatitis, and potential mechanistic insights that are important for demonstrating proof of concept.

4.3 JUSTIFICATION FOR DOSE

Dosing and bio-distribution data in humans show that pharmacological concentrations of vitamin C can only be attained following intravenous administration (32). Dosage selection for this trial was determined both from animal modeling, examining the biological effectiveness in a lung injury model system and from the recently conducted randomized double blind phase I human sepsis safety trial. The 200 mg/kg/24 hour IV dosing protocol was determined from quantification of plasma ascorbate levels and from assessing the impact on SOFA scores. Further, the dosage was selected following observation of the 200 mg/kg/24 hour regimen on biomarker levels.

4.4 END OF STUDY DEFINITION

Active treatment will continue until 96 hours, discharge from study hospital, study withdrawal, or death, whichever comes first. All subjects will be followed to day 90 for collection of outcomes data even though the study intervention will be completed by 96 hours from randomization at the latest.

5 STUDY POPULATION

5.1 INCLUSION CRITERIA

The inclusion and exclusion criteria listed for the CITRIS-AH trial are listed below. The definitions of alcoholic hepatitis and severe sepsis for this study are derived and defined as previously published in the reference literature.

Patients must have a diagnosis from the attending physician or hepatologist of definite or probable alcoholic hepatitis based on NIAAA criteria (2) and suspected or proven infection, and meet 2 out of 4 of the criteria for Systemic Inflammatory Response (SIRS) due to infection or be accompanied by at least 1 criterion for sequential organ failure assessment (SOFA):

1. Alcoholic hepatitis:
 - a. Definite NIAAA alcoholic hepatitis
 - i. Clinical diagnosis and histological confirmation of features of alcoholic hepatitis
 1. Histological diagnosis: liver biopsy with steatohepatitis, lobular inflammation, Mallory-Denk bodies, hepatocyte degeneration or ballooning, “chicken-wire” or portal fibrosis
 2. Clinical diagnosis:
 - a. Chronic alcohol use for at least 5 years (may be intermittent abstinent)
 - b. >1 standard drink per day in women and >2 in men
 - c. AUDIT score >15
 - d. Heavy alcohol use for at least 6 months
 - i. “Heavy use” = average >3 drinks per day (40g) for women and average 4 drinks (50-60g) per day for men
 - e. Onset of jaundice within the past 8 weeks
 - f. Less than 8 weeks of abstinence before onset of jaundice
 - g. Serum bilirubin >3 mg/dL
 - h. AST >50
 - i. AST/ALT ratio >1.5 and levels <400 IU/L
 - b. Probable NIAAA alcoholic hepatitis criteria
 - i. Clinical diagnosis based on heavy alcohol use >5 years
 - ii. Active alcohol use until 4 weeks prior to presentation
 - iii. average >3 drinks per day (40g) for women and average 4 drinks (50-60g) per day for men
 - iv. Sudden onset or worsening of jaundice (bilirubin >3 mg/dL) within past 60 days
 - v. AST/ALT ratio >1.5 and levels <400 IU/L
 - vi. Absence of other causes of liver disease
 1. Negative autoimmune markers (ANA < 1:160, SMA <1:80)
 2. Negative viral hepatitis markers (HAV A IgM, HBV sAg, HBV c IgM, HCV Ab, HCV RNA)
 3. No recent exposure to drugs with DILI potential, as determined by attending physician or hepatologist medication review
 - c. Patients with potential cofounders may be offered transjugular liver biopsy to assess for histological characteristics of alcoholic hepatitis and ruling out other features of chronic liver disease as a part of standard of care
2. Suspected or proven infection: (e.g., thorax, urinary tract, abdomen, skin, sinuses, central venous catheters, and central nervous system.)
3. The presence of a systemic inflammatory response: Defined as: fever: >38°C (any route) or hypothermia: <36°C (core temp only), tachycardia: heart rate > 90 beats/min or receiving medications that slow heart rate or paced rhythm, leukocytosis: >12,000 WBC/μL or leukopenia: <4,000 WBC/μL or >10% band forms. Respiratory rate > 20 breaths per minute or PaCO₂ < 32 or invasive mechanical ventilation.
4. The presence of sepsis associated organ dysfunction as assessed by SOFA: (any of the following thought to be due to infection)
 - a. Sepsis associated hypotension (systolic blood pressure (SBP) < 90 mm Hg or an SBP decrease > 40 mm Hg unexplained by other causes or use of vasopressors for blood pressure support (epinephrine, norepinephrine, dopamine =/> 5mcg, phenylephrine)
 - b. Arterial hypoxemia (PaO₂/FiO₂ ≤ 300) or supplemental O₂ > 6LPM.

- c. Lactate > upper limits of normal laboratory results
 - d. Urine output < 0.5 ml/kg/hour for > two hours despite adequate fluid resuscitation
 - e. Platelet count < 100,000 per mL
 - f. Coagulopathy (INR > 1.5)
 - g. Bilirubin > 2 mg/dL
 - h. Glasgow Coma Scale < 11 or a positive CAM ICU score
5. Negative urine or serum toxicology and acetaminophen drug screen

